Anthropometric and vital sign measurements: **Height** will be measured by a Stadiometer. **Weight** will be measured using a SECA Digital scale, and BMI (kg/m^2) will be calculated. **Waist circumference** will be measured using a flexible measuring tape. Participants will remain in a seated position for a minimum of 15 minutes prior to measurement of **resting heart rate** and **blood pressure** with an Omron Professional Digital blood pressure and heart rate monitor.

Concomitant medications: Participants will be instructed to bring all current medications (prescription, over the counter, and herbal or vitamin supplements) to each study visit. The research study coordinator will review and record these medications. Comorbidities: We will use patient self-report to document stroke, CVD (congestive heart failure, myocardial infarction, or coronary heart disease), peripheral vascular disease, peripheral neuropathy, renal disease, and retinopathy. Point of Care A1C: The DCA Vantage Analyzer tests for a quantitative determination of A1C in human whole blood and provides immediate test results from a finger prick of blood. If age <50 and female urine dipstick for pregnancy completed.

Pedometer: participants will be given a pedometer or if preferred use the one available on their smartphone. They will be asked to keep the pedometer or phone on them as much as possible during waking hours during the study. Data will be collected for 10 days after the first visit then for the 10 days prior for visits 2 and 3.

Continuous Glucose Monitoring:

Blinded CGM: All participants will undergo blinded CGM for 10 days at baseline a (2-4 weeks prior to start of education) and visit 3 (24 weeks [+/-2 weeks]). The blinded CGM- education group will also complete blinded CGM for 10-day period at the end of the education intervention (visit 2: study weeks12 [+/-2 weeks]). Participants can mail blinded CGM devices back in self-addressed postage-paid envelopes provided at the initial PN visit and devices will be provided at the first PN visit.

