RT-CGM: Participants in the RT-CGM arm will be asked to wear the device for a total of 50 days for 84 days during the 12 weeks of education sessions at intervals of 10 days on then 7 days off over 12 weeks. CGM data for 10 days will be downloaded after the completion of the 3rd RT-CGM wear session which should correlate approximately with the 6th education session. The final period of RT-CGM use will begin on the day of the final session of the DSMES curriculum. Participants will undergo initial training by PN and can have assistance for the first device self-insertion and may request additional virtual, telephone, or in-person assistance from PN. In our experience, study participants readily assimilate the self-insertion technique and require negligible follow-up support for this procedure. RT-CGM data will be collected remotely using a cloud-based platform

Preparation for the study intervention: Patient Navigators (PN) from Sea mar health education team will engage participants no more than 2-4 weeks prior to the start of the DSMES intervention to ensure participants have a working technology platform for the education sessions and provide hot spot if able through one home visit with option for second if need to assess barriers to technology or attendance. For all participants, PN will teach simple CGM insertion (blinded and RT). For those who are enrolled in RT-CGM arm, the PN will set up a mobile app for the RT-CGM device. PN also will conduct a 1, 30-minute training session on CGM for participants in this study, with particular focus on the use of RT-CGM as a tool to understand food and activity choices. If RC is remote PN may also engage at visits 1, 2 and 3 to gather objective measurements (weight, blood pressure and POC A1C or participant may go to LabCorp/quest for the A1C) As well they well gather the 10 days baseline pedometer data

Study Procedures: Study Participants' Household Member: No protected health information will be recorded for household member. Demographics of relationship to study participant, age and sex and history of diabetes or prediabetes will be recorded at baseline visit. Email address maybe recorded in order to contact patients if verbal permission is given.

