
The receiver and/or the app will display the glucose reading along with a rate of change arrow and a trend graph. Additionally, the receiver and/or app issues alarms and alerts to notify the patient of glucose level changes and other important system conditions. The app provides the additional capability to share data with "followers" using the Dexcom Share service.

CGM Ancillary Devices Dexcom CLARITY® is an accessory for users of the Dexcom CGM system. It is a software program that allows the transfer of glucose data from the CGM system to Dexcom remote servers for data management to allow the use of the CGM data by the user and study clinicians. Target ranges of 70 to 180 mg/dl will be set, and the patients will be introduced to the use of alarm settings. Both participants and study sites will use CLARITY® to transfer glucose data between user and study site, whether CGM is used in blinded or real-time mode. A CLARITY® mobile app can be used for a retrospective review of glucose data on the smart device and can also be set up to allow receipt of push notifications of CGM data facilitating data review. For all patients (intervention and control group) an anonymized CLARITY® account will be created by using a sequential study number which is allocated at randomization. Additionally, if participants desire The Dexcom G6 CGM System comes with a built-in Dexcom Share feature so you can let up to 10 people follow your glucose levels,

giving you a circle of support. By downloading the Dexcom Follow app, Followers can view your glucose data directly from their smart device

Intervention/ RT-CGM- education Group:

- For participants the DEXCOM G6 CGM app will be installed on participant's smart phone.
- An anonymized CLARITY® mobile account will be set up and linked to the research site.
- A high alert threshold will be set at 180 mg/dl and low alert threshold for <70mg/dl. In addition, the urgent low alert (55 mg/dl [3.1 mmol/l]), the urgent low soon alert (when glucose levels are falling fast and will be below 55 mg/dl [3.1 mmol/l] in less than 20 min) as well as alerts for rise and fall rate (3 mg/dl [0.17 mmol/l]) in addition to alerts for signal loss and no readings for more than 20 min will be enabled and patients will be shown how to turn off if they desire.
- Participants with applicable smart phones may have CLARITY® push notifications on the CLARITY® mobile app about weekly time in range comparison enabled during the study.

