N: Glucose/CGM Data /Evaluation Measures: For participants in both the education-only and RT-CGM study arms, the % time the CGM device was worn over each period of use will be captured. Glycemic outcome measures include time in range (TIR), mean glucose, coefficient of variation, mean amplitude of glucose excursion (MAGE), % time below range (TBR) (<70 mg/dL), and % time above range (TAR) (>180 mg/dL). Between-group comparisons for CGM-derived glycemic metrics will be assessed based on changes from baseline to study week 12 and baseline to study week 24.

O. Advisory Board: We will convene key stakeholders in an advisory board after approximately 20-25% of participants have completed the 12-week intervention and again during years 2 and 3 of the study. The first convening will occur after 1 education cycle has been completed for both an English- and Spanish-speaking cohort, with an estimated 20-30 participants having undergone the intervention. Key stakeholders will meet specifically to address barriers to entering and completing the education intervention, implementing the behavioral changes recommended by the DSMES curriculum, and adhering to CGM use in the RT-CGM arm of the study. Accordingly, invited stakeholders will include patients who were eligible but opted against participation, participants who enrolled but did not complete the intervention phase of the study, participants who completed the 12-week intervention, and participant's household member if desires. Additional stakeholders are described below. The board will be asked to assess possible barriers to participant engagement, including the following: support for technology use, adequacy of RT-CGM training, food insecurity, safety concerns, and time commitment and sustainability.

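### The week-12 CGM comparison sets live-display wear in one arm against blinded wear in the other, and should be labelled and reported as such

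*Combined protocol and SAP*

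**What the plan says.** Section N (Glucose/CGM Data/Evaluation Measures) lists time in range (TIR), mean glucose, coefficient of variation, MAGE, time below range (TBR, under 70 mg/dL) and time above range (TAR, over 180 mg/dL). It then states: "Between-group comparisons for CGM-derived glycemic metrics will be assessed based on changes from baseline to study week 12 and baseline to study week 24".

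The wear schedule is in Section H, Continuous Glucose Monitoring. For blinded wear it says "All participants will undergo blinded CGM for 10 days at baseline a (2-4 weeks prior to start of education) and visit 3", and then "The blinded CGM- education group will also complete blinded CGM for 10-day period at the end of the education intervention". No blinded wear at visit 2 is listed for the RT-CGM arm. That arm wears RT-CGM "at intervals of 10 days on then 7 days off over 12 weeks", for a planned total of 50 days, and "The final period of RT-CGM use will begin on the day of the final session of the DSMES curriculum". The Medical Devices section adds that its data are downloaded after the third and the fifth wear.

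On device settings for the RT-CGM group: "A high alert threshold will be set at 180 mg/dl and low alert threshold for <70mg/dl". An urgent-low alert at 55 mg/dl is also enabled, and participants are shown how to switch alerts off.

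The Data Analysis Plan (Section E, Aim 1) assigns the CGM indices, TIR among them, to descriptive between-group summaries. It also assigns TIR to a mixed model like the one for A1C, whose named fixed effects are an RT-CGM indicator and time (baseline, visit 2, visit 3).

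**The concern.** From baseline to week 12 the measuring condition changes in one arm only. Controls go from blinded to blinded. The RT-CGM arm goes from blinded to a live display, with default alerts at the two thresholds that define TBR and TAR. Complete data would not remove this difference, and neither would a mixed model.

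The randomised regimen is cyclic, so the off-device days are part of it. In weeks 1 to 12 no such day is recorded in the RT-CGM arm. If participants respond to the display and alerts mainly while wearing the sensor, the week-12 figure will look better than glycaemia over the full cycle.

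TIR is a named secondary outcome, and TBR is the only hypoglycaemia measure listed for comparison between arms. Without a label, a week-12 result could be read as more time in range, or less hypoglycaemia, under the programme as a whole. What it shows is glycaemia during one 10-day wear.

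**Working it through.** **Measuring condition by visit** (Section H, Continuous Glucose Monitoring; Medical Devices)

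| Time | Control arm | RT-CGM arm |
|---|---|---|
| Baseline | blinded | blinded |
| Week 12 (visit 2) | blinded | real-time, final wear, alerts on by default |
| Week 24 (visit 3) | blinded | blinded |

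Baseline to week 24 is like for like. Baseline to week 12 is not.

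**Off-device days.** Start the first wear on day 1 of the education period (assumption). Strict cycling of 10 on and 7 off puts the wears on days 1–10, 18–27, 35–44, 52–61 and 69–78. That is 5 × 10 = 50 days, which reproduces the plan's own figure. Off-device days are 84 − 50 = 34, or 34/84 = 40.5%.

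The plan also starts the last wear on the day of the final class. With weekly classes from day 1, class 12 falls on day 1 + 7 × 11 = 78, so that wear runs over days 78–87, of which 7 lie within the 84. Keeping the first four wears as above gives 4 × 10 + 7 = 47 days on and 37 off, or 37/84 = 44.0%. Off-device days are therefore about 34 to 37 of 84.

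**What can be said about size.** Let *g* be the average advantage of on-device over off-device days in the RT-CGM arm, and *s* the off-device share. The cycle average is the on-device mean less *s* × *g*, so on-device sampling overstates it by *s* × *g*. The documents give no value for *g*. The ranges below are assumptions to show scale only:

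- TIR, *g* = 0, 2, 5 or 10 percentage points: overstatement 0, 0.8, 2.0 or 4.0 points at *s* = 0.405, and 0, 0.9, 2.2 or 4.4 points at *s* = 0.440.
- TBR, *g* = 0, 0.25, 0.5 or 1.0 point: overstatement 0, 0.10, 0.20 or 0.40 point at *s* = 0.405. The last is about 6 minutes a day.

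If *g* is zero there is no overstatement, however many days go unsampled.

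**The TIR model.** The Aim 1 text names an arm indicator and visit as fixed effects, with no arm-by-visit term. As written, it does not define a visit-2 arm contrast (live display against blinded) apart from the visit-3 contrast (blinded against blinded). The Aim 3 text says the RT-CGM coefficient will be coded to give the average difference in 12-week change. It does not say how visit 3 is handled, and attaches no measuring condition.

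**Conflict between sections.** Specific Aim 1 and Section H both have controls wearing blinded CGM around visit 2. The Medical Devices section lists their wear at baseline and 24 weeks only. On that reading controls would have no week-12 CGM data, and the week-12 comparison could not be made.

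**The case against.** The strongest reply is that the display and alerts are the randomised intervention, so glucose recorded during their use is a legitimate on-treatment effect. Section N names a time point and nowhere promises an average over the on/off cycle. This stands: the week-12 contrast is valid for what it measures. What remains is that the plan does not say what it measures.

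Four stronger readings are tempting, and the documents support none of them.

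- A reader might turn the off-device share into an inflation factor for the treatment effect. That needs the ratio of off-device to on-device benefit, which is not given. Section C reports that the A1C response to 12 weeks of RT-CGM persisted over 12 months in the team's earlier study, so the gap could be small.
- A reader might say that controls, unlike the RT-CGM arm, are fully sampled. They have a single 10-day recording around week 12, and most of their days are unsampled too. The difference is that their days are all display-free, whereas the RT-CGM arm has two states and only one is recorded.
- A reader might infer that a false claim of less hypoglycaemia is planned. None is. Entry requires A1C of at least 8.0%, and prandial insulin is excluded, so TBR may be low and TIR the more affected index. Alerts can be switched off. The Medical Devices section also leaves unclear whether the alert below 55 sounds in blinded mode, so the alert contrast may be weaker than the settings suggest.
- A reader might conclude that week 24 should outrank week 12. Week 24 falls 12 weeks after RT-CGM ends and measures persistence. It does not estimate glycaemia over the cyclic regimen either.

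**Conclusion.** The week-12 between-arm comparison of TIR, TBR, TAR and the other CGM indices is not like for like. It is a valid effect while wearing RT-CGM, but the plan does not label it that way, and the TIR model does not separate it from the blinded visit-3 data. It may overstate benefit over the 10-on/7-off regimen, because about 34 to 37 of 84 days (40.5% to 44.0%) are off-device and unsampled in that arm. The direction is plausible, but the documents do not allow the size to be estimated. The day count rests on wear and weekly classes both starting on day 1.

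The A1C primary outcome is unaffected, and so is the week-24 CGM comparison. The point calls for a cheap change of wording and does not make the week-12 analysis invalid.

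**What to change.** In the Data Analysis Plan (Aim 1) and Section N:

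- Label the week-12 CGM contrast as *while wearing RT-CGM (unblinded) versus blinded control*.
- Estimate and report it separately from the baseline-to-week-24 contrast, for example with an arm-by-visit term in the TIR model. Identify week 24 as the like-for-like comparison, blinded in both arms at both times, of persistence after RT-CGM ends.
- State that no conclusion of lower hypoglycaemia or higher time in range over the whole cyclic regimen will be drawn from week 12 alone.
- Reconcile the Medical Devices section with Specific Aim 1 and Section H on the controls' week-12 blinded wear.

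The first three changes need wording only, with no new visit or sensor wear. The cost is a narrower week-12 claim.

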Participant Recruitment: A maximum number of 120 eligible patients **will be** enrolled (with goal 100 completed) and randomized from Sea Mar health centers. The study will recruit from 6 primary care clinics (Des Moines Medical Clinic, White Center Medical Clinic, Federal Way Medical Clinic, Kent Medical Clinic, Seattle Medical Clinic, Burien Medical Clinic) given the high volume of Latinx populations who receive care at these sites. Additional participants may come from other Sea Mar clinics, and from community engagement or the University of Washington clinics. Patients will be referred by their local primary care providers or by Sea Mar health education team and their review of patients with uncontrolled diabetes or new diagnosis of diabetes in the Sea Mar health system record. Patients who express interest will be contacted by telephone, email and/or in person by on-site research coordinators to ascertain interest and confirm eligibility criteria. Eligible individuals will be scheduled for their screening visit, ideally within 2 weeks of the contact.

Recruitment will be quarterly with one Spanish and one English speaking 12-week curriculum with a goal of 20-35 participants per DSMES cycle. We anticipate a roughly even distribution between English and Spanish speaking participants (e.g., 10-20 participants per cohort per language-specific curriculum cycle). A total of 4-6 DSMES cycles will need to be completed to reach 100 participants.

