AIM 1: Our primary endpoint for Aim 1 is the change in A1C from baseline to 12+/-2 weeks (end of the intervention period). Secondary outcomes include between-group differences in change in A1C at

24+/-2 weeks and changes in body weight, BMI, and blood pressure at 12+/-2 and 24+/-2 weeks. We will use simple descriptive statistics to quantify between-group differences in changes in CGM indices including TIR, mean glucose, mean amplitude of glycemic excursions, TAR, TBR, and coefficient of variation. The primary outcome of A1C will be assessed using a random-intercept random-slope linear mixed effects regression model that adjusts for an indicator of RT-CGM and time (baseline, visit 2, and visit 3) as fixed effects. To assess the effectiveness of the *Compañeros en Salud* curriculum, inference for Aim 1 will focus on the change in A1C from baseline to 12 weeks for the entire cohort (regardless of RT-CGM status). Secondary outcome measures of TIR, body mass index, waist circumference, and systolic/diastolic blood pressure will be similarly assessed using a generalized linear mixed effects model appropriate for each type of outcome measurement.

We will conduct a missing data analysis to describe and characterize enrolled participants who do not provide data due to attrition. Linear mixed effects models naturally handle intermittent missing data through maximum likelihood estimation. As described by Molenberghs and Kenward,⁴⁹ we will use inverse probability weighting in secondary analysis within each longitudinal regression model to inflate the weights of cases that are underrepresented in the analysis due to selective attrition and/or non-participation. We will also conduct sensitivity analyses using 10-fold multiple imputation to assess the robustness of the results when missing data are imputed. The characteristics of non-responders will be summarized in our final report, and we will present the sensitivity of the estimated treatment effect due to alternative missing data methods

Aim 2: For this Aim, the primary outcome will be the difference in % of DSMES education sessions attended for participants who complete the study before and after the stakeholder convening. Additional endpoints will similarly assess the differences in the following metrics of participant engagement: % adherence to RT-CGM use, % of participants who complete all study visits, and % of eligible patients who enroll in the study.

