Revisions to the study protocol that enhance access and engagement will be implemented for the remainder of the study period, and indices of engagement (% of eligible participants who enroll, % of education sessions attended, % of participants who complete all study procedures, % adherence to CGM use) will be measured prior to and after the changes implemented consequent to the stakeholder convening. Key stakeholders will be convened again in years 2 and 3 of the project. These meetings also will focus on barriers to sustaining the intervention, particularly with regard to the availability of essential resources (CGM devices; CDEs, health educations, PN, and other personnel; infrastructure to support remote education sessions, etc.) and therefore will be key for the design of future interventions.

Key stakeholders:

The advisory board will be chaired by [name], MD, Director of the UW Medicine Diabetes Institute LatinX Diabetes Clinic. Other members will include PN and members of Ventanillas de Salud (a local chapter with the Mexican consulate that works to combat health disparities). In addition, Spanish-speaking diabetes educators, primary care providers, and a quality improvement officer from Sea Mar will be included in the board. Ten participants from the first two cohorts (5 from each cohort of participants (with the goal to include 2 participants who withdrew from the intervention). We will ask

the first 3 participants who enrolled and completed greater than 70% of the sessions to be on the board. We will also ask the first 2 participants who stopped going to the sessions to be on the advisory board. If they decline we will continue to ask the next participant enrolled until we have 3 participants who have engaged in the educational sessions and 2 participants who stopped attending the sessions.

We hope to improve the diabetes classes and discuss any challenges people may be having with participating in the diabetes classes, and challenges with telemedicine sessions. We will ask questions either in a group setting or 1:1 tele-health interview about living with diabetes and any barriers/difficulties they are experiencing. Interviews will last approximately 50-60 minutes and will be recorded in order to ensure all answers are transcribed and then collated in a de-identified manner for QI for the program

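### Aim 2's before/after rule splits participants by study completion relative to the stakeholder convening, which does not match who was exposed to the revisions

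*Combined protocol and SAP*

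**What the plan says.** **The split in the analysis plan.** Section E, Data Analysis Plan, Aim 2, makes the primary outcome the "difference in % of DSMES education sessions attended for participants who complete the study before and after the stakeholder convening". The additional engagement measures are RT-CGM adherence and the percentages "of participants who complete all study visits, and % of eligible patients who enroll in the study".

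**The split in section O.** The Advisory Board section lists the same kind of indices but says they "will be measured prior to and after the changes implemented consequent to the stakeholder convening". It applies revisions to the rest of the study. It gives no effective date, no lag and no rule for participants who straddle the date. Further convenings are planned for years 2 and 3.

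**Timing of the board.** Section O states: "The first convening will occur after 1 education cycle has been completed for both an English- and Spanish-speaking cohort". It expects 20-30 people, about 20-25% of participants, to have been through the intervention by then.

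**Timing of participants.** Section D states: "Recruitment will be quarterly with one Spanish and one English speaking 12-week curriculum with a goal of 20-35 participants per DSMES cycle", and "A total of 4-6 DSMES cycles will need to be completed to reach 100 participants". In section H, the baseline visit (consent and randomisation) falls 2-4 weeks before the first class. The Randomization text caps baseline data at 3 weeks before. The Patient Navigator visit follows 10-14 days after baseline. Visit 3 is at week 24 +/- 2, twelve weeks after education ends.

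**The concern.** A before/after comparison is informative only if the before group met the old procedures and the after group met the new ones. Three different events are in play here: finishing the study, the board meeting, and the revisions taking effect. The analysis plan ties group membership to the first two. The effect of interest depends on the third.

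The board's remit includes barriers to entry, support for technology and the adequacy of RT-CGM training. Those steps take place at recruitment and in the navigator's preparation, weeks before a cohort's first class. A cohort can therefore have passed them under the old procedures and still be labelled as after.

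At stake is Aim 2's own primary comparison. Depending on the reading, it either has no before group or mixes unrevised participants into the after group, which would make a real improvement look smaller than it was.

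**Working it through.** **Plan's own figures.** Cycles needed = participants / cycle size, rounded up.
- 120 (maximum enrolment): 120/20 = 6 and 120/35 -> 4. This reproduces the stated 4-6.
- 100 (completion goal): 100/20 = 5 and 100/35 -> 3.
- First convening: 20% of 100 = 20 and 25% of 120 = 30. This reproduces the stated 20-30.

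**Calendar.** Week 0 is cycle 1's first class. Quarterly is taken as 13 weeks, with 12-week spacing in brackets. No pause between cycles is assumed.

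| Event | Week |
|---|---|
| Cycle 1 education ends; earliest first convening | 12 |
| Cycle 1 visit 3 | 22-26 |
| Cycle 2 baseline and randomisation (first class minus 4 to minus 2) | 9-11 [8-10] |
| Cycle 2 navigator visit (baseline plus 10-14 days) | 10.4-13 [9.4-12] |
| Cycle 2 first class | 13 [12] |

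Applying the 3-week cap on baseline data narrows cycle 2 baseline to weeks 10-11 [9-10], still before week 12.

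**Reading 1: finishing the study, as written.**
- Convening in weeks 12-21: no cycle 1 participant has reached visit 3. Before n = 0; after holds all 100-120, including cycle 1, whose classes were all unrevised.
- Convening at week 24: cycle 1 is part-way through its visit 3 window, and cycle 2 has already held 11 [12] of its 12 classes.
- Convening at week 26: cycle 1 can all be before, but cycle 2 has held all 12 classes unrevised and still counts as after.

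So, on this calendar, no convening date makes the groups match exposure.

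**Reading 2: finishing the 12-week intervention.** Before is cycle 1 and after is everyone else, including cycle 2. With equal cycles and, as the worst case, no cycle 2 exposure:

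unexposed share f = cycle size / (total - cycle size); observed gain = true gain x (1 - f)

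| Cycles x size | Before / after | f | True 10-point gain reads as |
|---|---|---|---|
| 4 x 25 | 25 / 75 | 25/75 = 33% | 6.7 |
| 5 x 20 | 20 / 80 | 20/80 = 25% | 7.5 |
| 4 x 30 | 30 / 90 | 30/90 = 33% | 6.7 |
| 6 x 20 | 20 / 100 | 20/100 = 20% | 8.0 |

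The 10-point gain is illustrative; the plan gives no target difference for Aim 2. The arithmetic also assumes that unrevised cycle 2 attends as cycle 1 did.

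**Completion of all visits.** For cycle 1 this depends on visit 3, 10-14 weeks after its education ends (22 - 12 = 10; 26 - 12 = 14). Revisions apply to the rest of the study, so part of a value labelled before can be produced after they start.

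**The case against.** **The schedule is inferred.** The overlap of cycle 2 with the convening needs cycles to run back to back. Section D states no pause, but does not rule one out. Figure 2 lists recruitment of the first 25, recruitment of the next 75 and the first convening as separate rows over six 6-month intervals. Its bars cannot be read in this text. Four to six quarterly cycles take about 12-18 months of those 36, so there is room for a gap. This stands, and makes reading 2 conditional. It does not rescue reading 1: a pause before cycle 2 does not bring cycle 1's visit 3 forward.

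**No implementation lag is stated.** Revisions might be live by cycle 2's first class, or introduced during it. Its classes would then be wholly or partly exposed, and the dilution smaller. This stands. Navigator preparation is also only mostly before the convening: a visit as late as week 13 could follow it.

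**The sentence can be parsed differently.** The time phrase might attach to sessions attended rather than to finishing the study. Cycle 1's classes would then be before. The cut would still be the convening, so cycle 2 classes held before the revisions would still be labelled after, as in reading 2.

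**Section O already has the better cut.** It does, but it conflicts with the analysis plan and does not classify straddlers.

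**A larger dilution is tempting.** Dividing a cycle of 20-35 by the 75 later recruits in Figure 2 gives 20/75 = 27% to 35/75 = 47%, so that a 10-point gain would read as 7.3 to 5.3. The upper end needs a cycle 2 of 35 after a cycle 1 of 25, which the plan does not state. These figures also do not describe the completion rule as written.

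**Conclusion.** The point holds. The analysis plan and section O define different cuts for Aim 2, and the analysis plan's rule gives a wrong grouping as written: with a convening before about week 22, the before group is empty and cycle 1's unrevised classes fall in after. That result rests only on the stated visit and convening times.

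On the intervention-completion reading, 20-33% of the after group could be unexposed, and a true 10-point gain would read as about 6.7-8.0. This is a worst case. It assumes back-to-back equal cycles, no cycle 2 exposure, and unrevised attendance equal to cycle 1's.

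A reader might infer that cycle 2 is certainly untouched by the revisions, or that every Aim 2 measure is biased towards no effect. The documents support neither. No effective date is given, and the week-24 issue concerns only completion of all visits, an additional measure. Nor does the point reach Aim 1: arms are randomised, and this split plays no part in that comparison.

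**What to change.** In the Data Analysis Plan, Aim 2, drop study completion relative to the convening as the grouping rule. Classify by exposure to the logged date on which each set of revisions takes effect, consistent with section O:
- **Enrolment:** by date of first approach.
- **Attendance and RT-CGM adherence:** by education cycle. A cycle is before if it ended before the effective date, and after if both its recruitment and its first class follow that date. Any other cycle is transitional and reported separately.
- **Visit completion:** report week 12 and week 24 separately, so that cycle 1's later follow-up is not mixed into a before value.
- **Year 2 and 3 convenings:** log and handle any further revisions in the same way.

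**Cost.** Wording in two sections, a short log of dates, and a smaller after group if a cycle is transitional. For equal cycles of 25, setting cycle 2 aside takes the after group from 75 to 50; for five cycles of 20, from 80 to 60. With 80% power, two-sided 0.05 and independent participants (class clustering ignored), the smallest detectable difference is 2.80 x sqrt(1/n1 + 1/n2) in SD units. It rises from 0.65 (25 v 75) to 0.69 (25 v 50), or from 0.70 (20 v 80) to 0.72 (20 v 60). That is a modest loss against a possible 20-33% dilution.
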